11. Subject has active liver disease, jaundice, elevated liver aminotransferases (ALT or AST), elevated total or direct bilirubin (DBL), elevated International Normalized Ratio (INR), or elevated alkaline phosphatase (ALP). Patients with mildly elevated ALT or AST up to 1.5 times the upper limit of normal (ULN) can be enrolled if total and DBL are normal. Patients with mildly elevated ALP (up to $1.5 \times$ ULN) can be enrolled if cholestatic liver disease is excluded and no cause other than fatty liver is diagnosed. Patients with Gilbert's syndrome with elevated TBL may be enrolled as long as DBL, hemoglobin, and reticulocytes are normal.
12. Subject has creatinine $> 1.5 \times$ ULN; or estimated glomerular filtration rate using the Modification of Diet in Renal Disease formula ≤ 59 mL/min per 1.73 m^2 at the screening visit.
13. Subject has a history of suicide attempt or suicidal behavior within the last 12 months or has suicidal ideation within the last 12 months (a response of "yes" to questions 4 or 5 on the suicidal ideation portion of the Columbia-Suicide Severity Rating Scale [C-SSRS]),

or who is at significant risk to commit suicide, as assessed by the investigator at screening and at the time of visit 2 (randomization).

14. Subject has previously been enrolled in a clinical trial with fezolinetant.
15. Subject is participating concurrently in another interventional study or participated in an interventional study within 28 days prior to screening, or received any investigational drug within 28 days or within 5 half-lives prior to screening, whichever is longer.
16. Subject is unable or unwilling to complete the study procedures.
17. Subject has any condition which, in the investigator's opinion, makes the subject unsuitable for study participation.
18. This criterion has been removed.
19. This criterion has been removed.
20. Subject has had a partial or full hysterectomy.

Waivers to the exclusion criteria will **NOT** be allowed.

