7.6.2 Laboratory Assessments

For quantitative laboratory measurements descriptive statistics will be used to summarize results and change from baseline for subjects in the SAF by treatment group and time point.

Shifts relative to normal ranges from baseline to each time point during treatment period in lab tests will also be tabulated. Laboratory data will be displayed in listings.

Number and percentage of subjects with platelets $< 150 \times 10^9/L$ will be separately summarized for each treatment group. The liver safety assessments will be summarized by the categories below based on the measurements from ALP, ALT, TBL, AST and their combination. These parameters will be based on measurements from a central laboratory.

The subject's highest value during the treatment period will be used.

- $ALT > 3 \times ULN, > 5 \times ULN, > 10 \times ULN, > 20 \times ULN$
- $AST > 3 \times ULN, > 5 \times ULN, > 10 \times ULN, > 20 \times ULN$
- $ALT \text{ or } AST > 3 \times ULN, > 5 \times ULN, > 10 \times ULN, > 20 \times ULN$
- $ALP > 1.5 \times ULN$
- $TBL > 2 \times ULN$
- $(ALT \text{ or } AST > 3 \times ULN) \text{ and } TBL > 2 \times ULN$
- $(ALT \text{ or } AST > 3 \times ULN) \text{ and } ALP < 2 \times ULN \text{ and } TBL > 2 \times ULN$

The last 2 criteria where 2 or more parameters are evaluated will be with the measurements on the same day or up to 1 day apart.

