10.2 Other Study Organization

A Liver Safety Monitoring Committee consisting of independent hepatologists experienced in the assessment of drug induced liver injury will be formed. This committee will conduct an independent review of individual subject cases that meet the individual withdrawal criteria pertaining to elevated transaminases or other liver health markers and advise the study sponsor whether the individual reviewed cases meet the criteria of a potential DILI. A separate charter will outline the activities of this committee.

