6.5.2.1 Liver Safety Assessment

The liver safety assessments will be summarized by the categories below based on the measurements from Alkaline Phosphatase (ALP), Alanine Transaminase (ALT), total

bilirubin, Aspartate Transaminase (AST) and their combination. These parameters will be based on measurements from a central laboratory.

The subject's highest value during the investigational period (from day of first dose of study drug until last dose of treatment period + 1 day) will be used.

- ALT > 3xULN, > 5xULN, > 8xULN, > 10xULN, >20xULN
- AST > 3xULN, > 5xULN, > 8xULN, > 10xULN, > 20xULN
- ALT or AST > 3xULN, > 5xULN, > 8xULN, > 10xULN, >20xULN
- ALP > 1.5 xULN
- Total Bilirubin >2xULN
- (ALT or AST > 3xULN) and Total Bilirubin > 2xULN
- (ALT or AST > $3 \times ULN$) and Total Bilirubin > $1.5 \times ULN$
- (ALT or AST > 3xULN) and ALP< 2xULN and Total Bilirubin > 2xULN

The last 2 criteria where 2 or more parameters are evaluated will be with the measurements on the same day or up to 1 day apart. The denominator for each criterion will be the number of subjects who have at least one value during the double-blind investigational period. The number and percentage of subjects meeting the criteria during the double-blind investigational period will be summarized by treatment group.

Due to COVID-19, patients might not be able to visit the clinical site and have clinical laboratory tests taken at the clinical site and evaluated by the central laboratory, in this case clinical laboratory tests can be taken by a local laboratory. The liver biochemistry safety assessments will be summarized including central and locally collected laboratory data due to COVID-19. This analysis is considered the primary analysis for the liver safety assessments.

The secondary analysis for liver biochemistry will be repeated by the data evaluated by the central laboratory but excluding the data that are impacted by COVID-19, which include the data recorded after the subjects were diagnosed of COVID-19, after study drug discontinuation due to COVID-19, during dose interruption due to COVID-19, and visits that are out of protocol window or data collected via home visits due to COVID-19 recorded in the eCRF.

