6.5.8 Subgroups of Interest for safety

The following factors are medically important subgroups for safety analysis: Race, smoking status, BMI category, NAFLD, and NASH. The data are being analyzed by subgroup are as follows:

- \circ Age (< 55 years, \geq 55 years): Treatment emergent AE (TEAE) table by SOC and PT, and Categorical Liver function table
- Race 1 (White, Non-White): Treatment emergent AE (TEAE) table by SOC and PT, and Categorical Liver function table
- Race 2 (White, Black, Asian, Other): Treatment emergent AE (TEAE) table by SOC and PT, and Categorical Liver function table
- Race 3 (Black, Non-Black): Treatment emergent AE (TEAE) table by SOC and PT, and Categorical Liver function table
- Geographical region (Europe, North American): Treatment emergent AE (TEAE) table by SOC and PT, and Categorical Liver function table

- Smoking Status(current, former/never, per substance use tabacco history CRF page): Treatment emergent AE (TEAE) table by SOC and PT, and Categorical Liver function table
- BMI category (>=18.5 kg/m² to <25 kg/m², >=25 kg/m² to <30 kg/m², >=30 kg/m²): Treatment emergent AE (TEAE) table by SOC and PT, and Categorical Liver function table
- Isolated non-alcoholic fatty liver disease (NAFLD) (Yes, No, per targeted medical history CRF page): Categorical liver function table
- Non-alcoholic steatohepatitis (NASH) (Yes, No, per targeted medical history CRF page): Categorical liver function table
- Diabetic Status (Yes, No): Categorical liver function table

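### The SAP liver table now has three combined criteria, but its same-day rule still covers only the last two, so the ALT/AST >3×ULN with TBL >2×ULN row loses its pairing

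*SAP*

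**What the plan says.** SAP 6.5.2.1 classifies subjects by ALT, AST, ALP and total bilirubin (TBL) thresholds. The rule placed ahead of the list is to use the subject's "highest value during the investigational period", which runs from first dose to one day after last dose. Eight rows follow, and the last three require a transaminase threshold and a bilirubin threshold together. The first of these three is the row for "ALT or AST > 3xULN) and Total Bilirubin > 2xULN". The timing rule comes after the list: "The last 2 criteria where 2 or more parameters are evaluated will be with the measurements on the same day", or up to one day apart.

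Protocol 7.6.2 contains the same highest-value rule and the same timing sentence, but its list has seven rows, of which only the last two are combined.

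**The concern.** The timing sentence appears to have been carried over from the protocol without being updated when a row was added. If so, the SAP withdraws the timing condition from a row that the protocol pairs, and does not say that it is doing so.

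That row matters. ALT or AST >3×ULN together with TBL >2×ULN is the severe category in Protocol 12.5. It is also the biochemical part of the Hy's Law description there, which asks for bilirubin and transaminase elevations to be concurrent. Two peaks months apart do not meet that description. Protocol 1.5 classes liver injury as an important potential risk, and Protocol 1.4.2 reports no Hy's Law cases in the phase 2b study. In a row expected to be empty or nearly so, a single spurious entry will draw attention.

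**Working it through.** **Step 1. Count the rows.** AT means ALT or AST; all thresholds are multiples of ULN.

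| Row content | Protocol 7.6.2 | SAP 6.5.2.1 |
|---|---|---|
| ALT; AST; ALT or AST; ALP; TBL, each alone | rows 1–5 | rows 1–5 |
| AT >3 and TBL >2 | row 6 | row 6 |
| AT >3 and TBL >1.5 | absent | row 7 |
| AT >3 and ALP <2 and TBL >2 | row 7 | row 8 |
| Rows covered by the timing rule (last two) | 6 and 7 | 7 and 8 |
| Combined rows left uncovered | none | row 6 |

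In the protocol the numeral 2 agrees with the list: two combined rows, both paired. In the SAP it does not: three combined rows, two paired. No other SAP section restores the pairing for row 6. The SAP's list of changes records one category added to 6.5.2.1 and no change to the timing rule.

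**Step 2. Apply the text to an invented subject.** ALT is 3.5×ULN on day 29 (week 4) with normal TBL. TBL is 2.2×ULN on day 281 (week 40) with normal ALT and AST. ALP is normal throughout. The gap is 281 − 29 = 252 days, against an allowance of 1 day.

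- Row 6, SAP as written (highest values): 3.5 > 3 and 2.2 > 2, so counted.
- Row 7 (paired): no qualifying pair, so not counted.
- Row 8 (paired): not counted.
- Row 6 under the protocol's rule: not counted.

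**Step 3. Check the nesting.** If all three rows are paired, every subject in row 8 is in row 6 and every subject in row 6 is in row 7, so row 8 ≤ row 6 ≤ row 7. With row 6 unpaired the second inequality can fail, as Step 2 shows.

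**Step 4. Bound the error.** Unpaired row 6 cannot exceed the smaller of the two single-condition counts, and paired row 6 cannot be below row 8. Hence

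overcount ≤ min(n[ALT or AST >3], n[TBL >2]) − n[row 8].

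One miscounted subject in a planned arm of 580 is 1/580 = 0.17 percentage points.

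**Step 5. Where the row appears.** There are two overall versions: the primary analysis, which adds local laboratory data collected because of COVID-19, and a second introduced by "The secondary analysis for liver biochemistry will be repeated by the data evaluated by the central laboratory". SAP 6.5.8 also asks for the "Categorical Liver function table" by subgroup. The levels are age 2, race 2 + 4 + 2, region 2, smoking 2, BMI 3, NAFLD 2, NASH 2 and diabetes 2, which makes 23. Total: 2 + 23 = 25 panels, assuming the subgroup tables are produced once. This shows where the row recurs; it does not measure bias, because one subject would recur across panels.

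**The case against.** **The sentence may be self-contradictory rather than wrong.** Its own description, criteria evaluating two or more parameters, fits all three combined rows, and the protocol still pairs row 6. SAP section 1 presents the SAP as an elaboration of the protocol's analysis. A programmer could infer the intent. It can also be said that the highest-value rule was meant only for single-parameter rows, so that row 6 is unspecified rather than unpaired. These readings are reasonable, but each requires setting aside the numeral or the rule that heads the whole list. The text names two of three rows, and two programmers could code it differently.

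**Few subjects are likely to be affected.** This largely stands. In phase 2b, 9 subjects had ALT or AST >3×ULN and none had TBL >2×ULN among 352 treated (Protocol 1.4.2 and 2.2.2). For a rough range, assume the two elevations are independent:

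- Two of the 179 subjects randomised to total daily doses up to 60 mg had the transaminase elevation: 2/179 = 1.1%.
- The one-sided 95% upper bound for 0/352 is 1 − 0.05^(1/352) = 0.85%.
- Per arm: 0.011 × 0.0085 × 580 ≈ 0.05 subjects. Scaling both 12-week rates by 52/12 ≈ 4.3 gives about 1.

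The observed bilirubin rate itself would give zero. The figure rests on independence and on extrapolating a 12-week study, so it is a guide only.

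**Gilbert's syndrome is weak support.** Protocol 3.3 says that subjects with Gilbert's "syndrome with elevated TBL may be enrolled as long as DBL, hemoglobin, and reticulocytes are normal", which makes a bilirubin peak apart from a transaminase peak plausible. But persistently raised bilirubin would also be raised on the day of a transaminase peak and so would count under the paired rule. Only intermittent values above 2×ULN cause a miscount, and the documents give no frequency for these.

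**The error hides no case.** True. It overcounts only, and row 8, which also requires ALP <2×ULN, remains paired. Protocol 10.2 sets up a panel of independent hepatologists: "This committee will conduct an independent review of individual subject cases that meet the individual withdrawal criteria pertaining to elevated transaminases" or other liver markers. Neither that review nor the stopping criteria uses this table.

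**Conclusion.** The concern holds. Followed as written, SAP 6.5.2.1 computes the ALT/AST >3×ULN with TBL >2×ULN row by a different rule from the protocol's, and the row cannot be compared with the paired rows beside it. One row of eight is affected, upward only, and the effect is probably small. The result may well be identical under either reading, but that depends on the data, and the documents do not allow the affected subjects to be counted. The conclusion rests on the literal numeral and on the highest-value rule applying to any row outside the timing rule. It should be corrected because it concerns a key liver-safety row. It does not threaten the trial's conclusions.

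**What to change.** In SAP 6.5.2.1, begin the timing sentence with *The last 3 criteria*, or name the three combined rows, so that each requires measurements on the same day or up to one day apart, as Protocol 7.6.2 does for its two. Check that the table specifications carry the same rule. The cost is one word, with no new data, tables or analyses. If the SAP is already final, the correction can be recorded in the clinical study report, as SAP section 1 provides.

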6.5.3 Vital Signs

Vital signs (systolic blood pressure, diastolic blood pressure and pulse rate) and BMI and weight will be summarized using mean, standard deviation, minimum, maximum and median by treatment group and visit. Additionally, a within-subject change will be calculated per visit as the post-baseline measurement minus the baseline measurement and summarized by treatment group and visit.

6.5.4 Electrocardiograms

ECG variables will be summarized using mean, standard deviation, minimum, maximum and median for each treatment group at each treatment visit, including changes from baseline. If multiple ECG variable values are available in one visit, use the mean value.

Number and percent of subjects with normal and abnormal results as assessed by central reader for the 12 lead ECG will be tabulated by treatment group at each treatment visit.

The QTc interval will be summarized using frequency tables for each treatment visit for values of clinical importance using the range criteria below.

	QTc Interval Criteria Value (msec)
Normal	\leq 450
Borderline	> 450
Prolonged	> 480
Clinically significant	> 500

Number and percent of subjects with 12 lead ECG abnormalities as well as number and percent of subjects whose 12 lead ECG reading changed from normal at baseline to abnormal will be tabulated by treatment group at each treatment visit.

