6.5 Analysis of Safety

Overall long-term safety of fezolinetant and the effect of fezolinetant on endometrial health will be the primary objective of this study. The safety assessments include adverse events, laboratory assessments, vital signs, C-SSRS, ECG, endometrial health assessment and imaging (mammogram, DXA, TVU). In all analysis of safety, the treatment group includes placebo, fezolinetant 30mg, fezolinetant 45mg and fezolinetant total will be presented by treatment group for SAF, unless specified otherwise. For analyses by visit, the analysis windows from Section 6.10.1 will be applied. Except for adverse events and follow-up visit data, only data up to one day after the last dose date will be considered for the analyses.

The baseline value for safety endpoint will be the last non-missing value taken on or prior to first dose of study drug unless otherwise noted.

Primary Safety Variables

- Frequency and severity of AEs.
- Percentage of subjects with endometrial hyperplasia.
- Percentage of subjects with endometrial cancer.

Secondary Safety Variables

- Change from baseline in endometrial thickness at 12 months.
- Percentage of subjects with disordered proliferative endometrium.
- Change from baseline in bone mass density (BMD) and trabecular bone score (TBS) at hip and spine at 12 months.
- Change from baseline to each timepoint in vital signs: sitting systolic and diastolic blood pressure and pulse rate.

- Change from baseline to each timepoint in laboratory tests: hematology, biochemistry and urinalysis.
- C-SSRS at each timepoint.
- Change from baseline to each timepoint in ECG parameters

Exploratory Safety Variables

- Change from baseline to specified time points in serum concentrations of sex hormones and sex hormone-binding globulin (SHBG) (week 4, 12, 24, 52 and 55).
- Plasma concentration of fezolinetant and the fezolinetant metabolite ESN259564 at specified timepoints (week 4, 12, 24 and 52).

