6.10 Additional Conventions

6.10.1 Analysis Windows

Study Day for analysis windows will be calculated as date of visit/assessment – first dose date +1.

Study Day for the follow-up (FUD) phase will be calculated as date of visit/assessment – last dose date of study treatment (Date of EOT).

Except for adverse events, for the analysis window (weeks prior to the follow-up period), the last day is always 1 day after the last day of exposure to double-blind treatment.

The end of overall treatment is defined as the last day of treatment +1 and the follow-up period begins at last overall treatment + 2 days and onward (Follow-up Study Day 2).

The data summary by visits will be done following the analysis windows specified in the table below:

Analysis	Scheduled	Analysis Windows (day)				
Visits	Day in Protocol	a)	b)	c)	d)	e)
Baseline	Day 1	Last non-missin	ng value on or prio	or to day 1 (inclu	sive)	
Week 2	Day 15	2 to 22				
Week 4	Day 29	23 to 43	2 to 43	2 to 57		
Week 8	Day 57	44 to 71	44 to 71			
Week 12	Day 85	72 to 99	72 to 99	58 to 127	2 to 127	
Week 16	Day 113	100 to 127	100 to 127			
Week 20	Day 141	128 to 155	128 to 155			
Week 24	Day 169	156 to 183	156 to 183	128 to 267	128 to 267	
Week 28	Day 197	184 to 211	184 to 211			
Week 32	Day 225	212 to 239	212 to 239			
Week 36	Day 253	240 to 267	240 to 267			
Week 40	Day 281	268 to 295	268 to 295			
Week 44	Day 309	296 to 323	296 to 323			
Week 48	Day 337	324 to 351	324 to 351			
Week 52	Day 365	352 to 376	352 to 376	268 to 376	268 to 376	2 to 376
Follow-up	Day 386	Last treatment + 2 days and onwards				

a) Apply to Clinical laboratory and urinalysis

b) Apply to Vital signs

- c) Apply to Blood PD/PK sample, EQ-5D-5L, MENQoL
- d) Apply to C-SSRS
- e) Apply to 12-lead ECG

For TVU and DXA, the week 52 analysis window is day 2 to last treatment + 30 days. For endometrial biopsy, refer to Section 6.5.5 for analysis window.

As a general rule, if more than one observation exists within the analysis window, the observation closest to the scheduled visit day will be selected for that visit. If there are two observations that have the same distance from the scheduled day, the value that is after the scheduled day will be selected in the analysis. If more than one observation is made on the same day, an average value if continuous or the worst value if categorical will be included in the analysis.

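### The SAP does not say which multiple-reading rule governs the QTc category table, and no ECG table counts each woman's highest on-treatment QTc, so a single value above 500 msec can go uncounted

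*SAP*

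**What the plan says.** SAP 6.5.4 opens with descriptive statistics for ECG variables at each treatment visit, including change from baseline. That paragraph ends: "If multiple ECG variable values are available in one visit, use the mean value". After a paragraph on central-reader results, the section adds: "The QTc interval will be summarized using frequency tables for each treatment visit for values of clinical importance using the range criteria below". The categories are ≤450 (normal), >450 (borderline), >480 (prolonged) and >500 msec (clinically significant).

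SAP 6.5 links by-visit safety analyses to the windows: "For analyses by visit, the analysis windows from Section 6.10.1 will be applied". In the SAP 6.10.1 table, the column footnoted "Apply to 12-lead ECG" has one post-baseline entry, Week 52, covering Day 2 to Day 376. SAP 6.5 also sets the upper limit for data other than adverse events and follow-up visit data: "only data up to one day after the last dose date will be considered for the analyses".

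For several readings in a window, the general rule in SAP 6.10.1 is: "if more than one observation exists within the analysis window, the observation closest to the scheduled visit day will be selected for that visit". For ECG the scheduled day is Day 365. The same paragraph deals separately with several readings on one day: continuous values are averaged, and for categorical values the worst is taken.

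Protocol Table 1 schedules the 12-lead ECG at screening and at the Visit 15/EOT/ED column only, so there is one scheduled post-baseline ECG. Footnote c to that table allows unscheduled visits.

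**The concern.** A threshold table for QTc exists to count extremes. It does that reliably only if the value categorised for each woman is her highest one, or if she has only one. Here the value may be a mean or may be the reading nearest Day 365, and neither rule is designed to retain an extreme. The maximum in the descriptive table does not fill the gap, because it too is taken over one value per woman per visit.

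ECG parameters are a named secondary safety endpoint in a trial whose primary objective is long-term safety. Elsewhere the SAP protects extremes. Liver categories in 6.5.2.1 use each woman's highest value through last dose + 1 day. Laboratory shifts in 6.5.2 use the worst finding during treatment. Where several post-baseline biopsies include an abnormal final diagnosis, 6.5.5 counts the more severe result. ECG is the exception. The current SAP has no change-from-baseline QTc outlier table, so the threshold table is the only QTc-specific categorical summary.

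**Working it through.** The plan states no QTc rate, power or precision figure, so there is nothing of its own to reproduce. The check classifies assumed QTc sets under each rule that the text could support. All msec values are assumptions, because the documents give no QTc data.

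**Rules**
- A: mean of all readings from Day 2 to Day 376 (SAP 6.5.4, with visit read as the analysis window).
- B: reading closest to Day 365, with same-day readings averaged (SAP 6.10.1, QTc treated as continuous).
- C: reading closest to Day 365, with the worst same-day reading taken (SAP 6.10.1, QTc category treated as categorical).
- D: highest on-treatment reading (the principle in SAP 6.5.2.1).

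| Assumed readings (msec) | A | B | C | D |
|---|---|---|---|---|
| Day 100 = 510, Day 365 = 440 | (510+440)/2 = 475, >450 | 440, ≤450 | 440, ≤450 | 510, >500 |
| Day 365 = 510 and 440 | 475, >450 | 475, >450 | 510, >500 | 510, >500 |
| Day 365 = 520, 430, 430 | 1380/3 = 460, >450 | 460, >450 | 520, >500 | 520, >500 |
| Day 60 = 505, Day 200 = 430, Day 365 = 420 | 1355/3 = 451.7, >450 | 420, ≤450 | 420, ≤450 | 505, >500 |
| Day 100 = 440, Day 365 = 510 | 475, >450 | 510, >500 | 510, >500 | 510, >500 |

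Of these five women, each with one reading above 500, the >500 row counts none under A, one under B, three under C and five under D. The sets were chosen to show how the rules behave, so these counts are not estimates of frequency.

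**How easily averaging moves a value.** With one other reading x, a peak P stays above 500 only if (P + x)/2 > 500, that is x > 1000 − P.
- P = 510 leaves the >500 row if x ≤ 490, and falls to 480 or below if x ≤ 450.
- P = 520 leaves the >500 row if x ≤ 480.
- If x = 430, P must exceed 1000 − 430 = 570 to stay.

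**Direction.** Neither a mean of readings nor one selected reading can exceed the highest reading. Under A, B or C the >500 count is therefore equal to or below the count under D. Between A and B the direction is not fixed. With Day 100 = 520 and Day 365 = 445, A gives 482.5 (>480) and B gives 445 (≤450). With 580 and 440 on those days, A gives 510 (>500) and B gives 440 (≤450).

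**The case against.** A reader might infer that the SAP averages every tracing from Day 2 to Day 376 and then sorts the result into the QTc rows. The documents do not say that. The averaging sentence closes the paragraph on continuous summaries, the frequency table comes later without mentioning an averaged value, and visit is not defined as the window. The two sections can be read together: 6.10.1 selects the ECG for the window, and 6.5.4 averages replicates at that visit. The wide window also has an evident purpose, since the Visit 15 column serves early discontinuation, which can fall on any day. All of this stands. What remains is that the text does not settle the rule, and that the harmonising reading still drops an outlier recorded on another day.

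The same-day provision in 6.10.1 may keep an outlier recorded on the selected day, if the QTc category is treated as categorical. That also stands, although QTc in msec is continuous and the text leaves the choice open.

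A reader might also suppose that extra tracings come mainly from women with symptoms or abnormal readings. That is plausible, but no section gives the number of extra ECGs or the reasons for them.

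Finally, extremes have other routes into the report. Protocol 5.8.1.1 requires clinically significant ECG abnormalities not related to underlying disease to be reported as adverse events. SAP 6.5.4 tabulates central-reader abnormal results and normal-to-abnormal changes. Protocol 7.6.5 lists all ECG interpretations. This cover is real but partial: the central-reader tables are also by visit and are not specific to QTc, an adverse event depends on the investigator's judgement, and a listing gives no count by arm.

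**Conclusion.** The point holds as a gap in specification with a known direction. The SAP leaves open which multiple-reading rule feeds the QTc categories, and no ECG table counts the highest on-treatment value. A QTc above 500 msec on a day other than the selected ECG can leave the >500 row under either rule; in the Day 100 = 510, Day 365 = 440 example, it becomes 475 or 440. A same-day outlier may or may not be kept. Relative to a highest-value count, the tabulated count is equal or lower.

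Two stronger conclusions are not supported: that the SAP prescribes averaging across the whole window before categorisation, and that its rules can only lower the count whatever the comparison. The second is true only against the highest value.

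The likely effect is small and the severity low. One post-baseline ECG is scheduled, so only women with repeat or unscheduled tracings are exposed. That they will be few is an assumption, because the documents give no count. The msec examples are assumed as well.

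**What to change.** In SAP 6.5.4:
1. Limit averaging to replicate tracings at the same time point, and state that it applies only to the mean and mean-change summaries.
2. Add an any-time-on-treatment row to the QTc threshold table, based on each woman's highest post-baseline QTc through last dose + 1 day and including unscheduled ECGs. This matches the highest-value principle already used for liver tests in 6.5.2.1.
3. State which rule supplies the value for the by-visit QTc categories, so that 6.5.4 and 6.10.1 cannot be applied differently to the same woman.

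The cost is SAP wording and one derived variable, with no new data collection. Outlier counts may rise slightly. This is a cheap improvement.
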